11.4 Data disclosure

11.5 Data safety and monitoring

11.6 Risk/benefit

11.6.1 Potential study risks

11.6.2 Potential study benefits

11.6.3 Risk/benefit assessment

1. Abstract

Cardiovascular (CV) events are the leading cause of mortality in the United States. Statins have been demonstrated to be an effective tool for reducing CV events and mortality, but statins are often not prescribed for patients that meet evidence-based guidelines. In this study, we will evaluate a health system initiative using active choice to identify eligible patients and prompt primary care physicians to initiate statin prescription. In partnership with the health system, this will be conducted as a randomized, controlled trial to evaluate its effect

2. Overall objectives

The objective of the study is to evaluate the effect of a health system initiative using active choice with and without social comparisons feedback to encourage physicians to prescribe statins for patients that meet evidence-based guidelines.

3. Aims

3.1 Primary outcome

The primary outcome measure is the change in percentage of eligible patients prescribed a statin medication within 2 months of intervention completion.

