5.1 Design

This study will use a randomized, controlled trial to evaluate a health system initiative. The electronic health record will be used to generate lists of patients who meet criteria for statin prescription using the 2013 ACC/AHA (American College of Cardiology / American Heart Association) guidelines. Primary care physicians at the University of Pennsylvania Health System will be randomly assigned to a control group with no intervention or one of two intervention groups as follows:

--Intervention 1: Active choice--

Primary care physicians will be prompted by email to review an online form with a list of their patients who are eligible for statin therapy but have not been prescribed one. Clinical information including the following will be presented for each patient (as available): age, history of atherosclerotic cardiovascular disease (ASCVD) or diabetes, recent test results including lipid profiles and liver function tests. If appropriate information is available, the ASCVD risk score will be calculated and displayed.

Using the form, the physician will be able to select atorvastatin 20mg for all of the patients or can individually review information for each patient and select from the following options: 1) prescribe atorvastatin 20mg once daily; 2) prescribe atorvastatin at a different dose (10mg, 40mg or 80mg); 3) prescribe a different statin (choose from simvastatin, pravastatin, or rosuvastatin); 4) do not prescribe a statin and select a reason (patient declined; patient allergy; other).

The online form will be created using a HIPAA compliant website on secure University of Pennsylvania Health System servers. The website will require the physician to sign in using their PennKey and password. Once the form is submitted, a member of the study team will enter the orders in EPIC for the physician to review and sign. The physician will receive notification that these orders have been entered and are ready to review. A letter to the patient will be generated describing the physician's review of their information, prescription of a statin, and the risks and benefits of taking a statin medication.

--Intervention 2: Active choice and social comparisons—

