5.4 Accrual

Primary care physicians at the University of Pennsylvania Health System will be randomly assigned to one of the three arms. Based on an initial data review, we have made the following assumptions: baseline statin initiation rate is about 65%, median number of patients eligible but not on a statin per primary care physician is 38, intracluster correlation for statin prescribing is 0.026. Given these baseline, we estimate that a sample size of 84 primary care physicians (28 per arm) will provide at least 90% power to detect a 10% difference between each intervention arm and the control arm, using a Bonferroni correction to define an alpha of .017 (three comparisons) as our threshold for statistical significance.

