5.5 Key inclusion criteria

Patients must meet the following criteria to be eligible for the study:

1) Have a primary care physician at the University of Pennsylvania Health System; 2) Meets American College of Cardiology / American Heart Association (ACC/AHA) guidelines for statin prescription as follows: a) Any form of atherosclerotic cardiovascular disease (ASCVD); b) LDL-C levels of 190 mg/dL or greater on their most recent lipid panel; c) Age 40 to 75 years with diabetes and LDL-C levels of 70-189 mg/dL on their most recent lipid panel; d) Age 40 to 75 years with 10-year ASCVD risk of 7.5% or greater.

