5.6 Key exclusion criteria

Patients will be excluded if any of the following criteria is met: 1) Allergy to statins; 2) Severe renal insufficiency defined as glomerular filtration rate (GFR) less than 30 mL/min; 3) Adverse reaction to statins including a) myopathy, ICD-10 G72.0 G72.9, ICD-9 3594 3599; b) Rhabdomyolysis, ICD-10 M62.82, ICD-9 72888; c) hepatitis, ICD-10 K716, ICD-9 5733

Physicians (and their respective patients) will be excluded if they have less than 10 patients among their entire panel that are eligible for a statin medication.

6. Subject recruitment

Information on primary care physicians and their patients at the University of Pennsylvania Health system will be obtained from the electronic health record using Penn Data Store and Clarity, an EPIC reporting database.

7. Subject compensation

No compensation will be offered in this study.

8. Study procedures

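### The primary outcome is worded over all eligible patients, but the prompt reaches only those not yet on a statin, so on the likely reading of 5.4 an absolute effect on new prescribing is reported at about a third of its size.

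*Combined protocol and SAP*

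**What the plan says.** The primary outcome in 3.1 is: "The primary outcome measure is the change in percentage of eligible patients prescribed a statin medication within 2 months of intervention completion". The main analysis in section 9 uses the same denominator and compares before with after by unadjusted chi-square tests.

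Eligibility in 5.5 rests on having a system primary care physician and on guideline criteria: "Meets American College of Cardiology / American Heart Association (ACC/AHA) guidelines for statin prescription as follows". Being off a statin is not required. The exclusions in 5.6 ("Patients will be excluded if any of the following criteria is met: 1) Allergy to statins", then severe renal insufficiency and adverse reactions) do not include current statin use.

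The intervention in 5.1 presents each physician with "a list of their patients who are eligible for statin therapy but have not been prescribed one".

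The planning inputs in 5.4 include "baseline statin initiation rate is about 65" per cent, "median number of patients eligible but not on a statin per primary care physician is 38" and "intracluster correlation for statin prescribing is 0.026".

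Physicians are excluded by 5.6 "if they have less than 10 patients among their entire panel that are eligible for a statin medication".

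**The concern.** The population scored and the population acted on differ. A patient already on a statin is never listed and cannot become a new prescription. Such a patient can change the outcome only by stopping, which the prompt does not address. Including these patients shrinks the reported absolute effect and, where some of them stop, adds noise.

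Two further places show the same mismatch. Section 5.4 appears to combine a cluster size from the untreated population with a rate from the whole eligible population. The physician minimum in 5.6 counts all eligible patients, so a physician whose 10 eligible patients are all treated would enter with an empty form.

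At stake are how the result reads, whether the 10-point target means what its authors intended, and, depending on how section 9 is carried out, power.

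**Working it through.** **Inputs from the documents.** 28 physicians per arm, 38 untreated patients per physician, a rate of 65%, ICC 0.026 and a 10% difference (5.4); two-sided alpha 0.017 for three comparisons (5.4, section 9), used below as 0.05/3, z = 2.394.

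**Assumptions.** The 65% is the share of eligible patients already treated. The 10% is absolute. One ICC serves both populations. Control initiation among untreated patients is 5%; the documents give no figure.

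**1. The plan's own power.** Design effect = 1 + (m − 1) × ICC; effective n per arm = 28m / design effect; SE = √{[p₁(1−p₁) + p₂(1−p₂)] / effective n}; power = Φ(difference/SE − 2.394).

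- m = 38: design effect 1 + 37 × 0.026 = 1.962; effective n = 1064/1.962 = 542.
- 65% vs 75%: SE 0.0277; power = Φ(3.615 − 2.394) = 88.9%, close to the stated 90%.
- m = 38/0.35 = 108.6 (all eligible): design effect 3.797; effective n = 3040/3.797 = 801; SE 0.0228; power 97.7%.

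The stated figure fits best when 38 untreated patients are paired with the 65% rate.

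**2. Dilution.** If the prompt does not affect treated patients, effect over all eligible = (1 − 0.65) × effect among listed = 0.35 × effect among listed. The factor is 0.45 at a baseline of 55% and 0.25 at 75%.

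- 10 points among listed patients → 0.35 × 10 = 3.5 points.
- 10 points over all eligible → 10/0.35 = 28.6 points among listed patients.

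**3. Power if post-period percentages are compared.**

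| Initiation, control vs prompt | All eligible (m = 108.6) | Untreated only (m = 38) |
|---|---|---|
| 5% vs 15% | 66.75% vs 70.25%, SE 0.0232, power 19% | SE 0.0180, power over 99% |
| 5% vs 10% | 66.75% vs 68.5%, SE 0.0234, power 5% | SE 0.0159, power 77% |

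The all-eligible percentages are 65 + 0.35 × initiation.

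**4. Power if change is analysed by physician.** If no treated patient stops and the treated share is the same for every physician, the change over all eligible is 0.35 × the untreated percentage. Effect and SE shrink together and the test statistic is unchanged. To allow for variation and stopping, I simulated 28 physicians per arm with 109 eligible patients each, beta-binomial clustering at ICC 0.026, and a t-test on each physician's change at alpha 0.017 (20,000 replicates).

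| Stopping among treated patients | 5% vs 15% | 5% vs 10% |
|---|---|---|
| None | over 99% | about 70% to 72% |
| 2%, independent between patients | about 99% | about 55% |
| 5%, independent between patients | about 94% to 95% | about 42% |
| 2%, clustered by physician | about 94% | about 43% |
| 5%, clustered by physician | about 80% | about 25% |
| Untreated patients only | over 99% | about 75% |

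Post-period comparison in the same simulation gave about 19% and 5%, agreeing with step 3.

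**The case against.** The strongest reply is that 3.1 and section 9 define a change, and section 8.2 stratifies randomisation by quartile of baseline prescribing rate. A reader of step 3 might infer that a prompt that triples new prescribing would probably be declared to have no effect. The documents do not support that. The 19% belongs to a post-period comparison, and a paired change analysis of 5% vs 15% keeps high power unless stopping is fairly common and clusters by physician. This objection stands. What remains is that section 9 names unadjusted chi-square tests, does not say how they apply to a change, and specifies no paired method; its regression is only a robustness check.

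Second, the denominator is not beyond dispute. Section 5.4 calls the 65% an initiation rate, and the abstract uses eligible for patients in whom a statin is to be started. Against this, 5.4 separately describes patients who are eligible but not on a statin, section 8.2 stratifies on baseline prescribing, and section 9 adjusts for baseline statin status, which has no use if everyone analysed is untreated. The reading is well supported, but it is an inference.

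Third, coverage among guideline-eligible patients is a legitimate health-system measure. Dilution of an absolute effect is not bias against the outcome as defined. Nor can one infer that the trial is underpowered for its declared target: 10 points over all eligible patients has about 98% power in step 1. Nothing in the documents shows that a 29-point conversion is out of reach, since 5.1 allows one selection for all listed patients. All of this stands.

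Fourth, with a median of 38 untreated patients, a physician with an empty form is a rare case. That also stands.

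**Conclusion.** The mismatch is real on the text. If 65% of eligible patients are already treated, an absolute effect on new prescribing is reported at 0.35 of its size, and the 10-point target corresponds to about 29 points among listed patients. That follows from the wording and the 65% alone.

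The effect on power is conditional. It rests on initiation and stopping rates that the documents do not give, on panel sizes obtained by dividing a median by an overall rate, and on one ICC for two quantities. The loss is severe under a post-period comparison. Under a paired change analysis it is small for 5% vs 15% in most of the cases tried, and material for 5% vs 10% once treated patients stop.

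Scoring untreated patients remains the better choice. It aligns the outcome with the intervention and with the cluster size in 5.4, removes noise from stopping, and does not depend on how an unspecified chi-square is applied to a change. The point is one that should be fixed; it does not invalidate the trial.

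**What to change.** - **3.1 and section 9:** define the primary outcome as the percentage of patients eligible and not on a statin at randomisation who are prescribed one by the 2-month cut-off, compared between arms with clustering by physician. Fix the list at randomisation in the same way in all three arms.
- **3.2:** keep the change over all eligible patients as a secondary outcome; none is listed now. State how change is tested.
- **5.4:** say what the 65% measures, and redo the calculation with a control initiation rate, and an ICC if one can be obtained, for the untreated population.
- **5.6:** apply the physician minimum to patients who are eligible and untreated. This is a minor correction.

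The cost is protocol wording before data extraction; 5.1 already has the lists built from the electronic record. The headline result will no longer read as overall statin coverage, though the secondary outcome keeps that figure, and a few physicians with very few untreated patients will drop out.

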3.2 Secondary outcome

Not applicable

4. Background

Statins, or HMG-CoA reductase inhibitors, are an effective and well tolerated treatment for hyperlipidemia and reduce CV event occurrence and mortality.^{1,2} However, despite their demonstrated clinical utility and wide acceptance, statins are underutilized and not prescribed to many patients who would benefit from them under current guidelines.³ In a recent study looking at the diabetic population, only about 35% of patients who were eligible and lacked contraindications for a statin were prescribed a statin.⁴

In 2013, the American Heart Association and the American College of Cardiology created a new method of estimating 10-year cardiovascular disease (CVD)⁵. They also concurrently released new guidelines for statin prescription that used a combination of age, low-density lipoprotein cholesterol (LDL-C) levels, diabetes diagnosis, and 10-year CVD diagnosis to establish clinical benefit of statins.⁶ Although this patient information is readily available to primary care physicians, clinicians are not often presented with the relevant clinical information in a streamlined manner that aids making decisions about a particular guideline.

Active choices, or compelling people to make a decision between alternatives, have been demonstrated to increase compliance to a beneficial intervention and may offer an opportunity to

increase statin prescription initiation.^{7,8} Social comparisons feedback has also been demonstrated to change physician behavior in many contexts including antibiotic prescribing.⁹

References

- [1] Robinson JG. Accumulating evidence for statins in primary prevention. *JAMA*. 2013;310(22):2405-2406.
- [3] Hirsh, B. J., Smilowitz, N. R., Rosenson, R. S., Fuster, V., and Sperling, L. S. (2015). Utilization of and adherence to guideline-recommended lipid-lowering therapy after acute coronary syndrome: opportunities for improvement. *J. Am. Coll. Cardiol.* 66, 184–192.

5.1 Design

This study will use a randomized, controlled trial to evaluate a health system initiative. The electronic health record will be used to generate lists of patients who meet criteria for statin prescription using the 2013 ACC/AHA (American College of Cardiology / American Heart Association) guidelines. Primary care physicians at the University of Pennsylvania Health System will be randomly assigned to a control group with no intervention or one of two intervention groups as follows:

--Intervention 1: Active choice--

Primary care physicians will be prompted by email to review an online form with a list of their patients who are eligible for statin therapy but have not been prescribed one. Clinical information including the following will be presented for each patient (as available): age, history of atherosclerotic cardiovascular disease (ASCVD) or diabetes, recent test results including lipid profiles and liver function tests. If appropriate information is available, the ASCVD risk score will be calculated and displayed.

Using the form, the physician will be able to select atorvastatin 20mg for all of the patients or can individually review information for each patient and select from the following options: 1) prescribe atorvastatin 20mg once daily; 2) prescribe atorvastatin at a different dose (10mg, 40mg or 80mg); 3) prescribe a different statin (choose from simvastatin, pravastatin, or rosuvastatin); 4) do not prescribe a statin and select a reason (patient declined; patient allergy; other).

The online form will be created using a HIPAA compliant website on secure University of Pennsylvania Health System servers. The website will require the physician to sign in using their PennKey and password. Once the form is submitted, a member of the study team will enter the orders in EPIC for the physician to review and sign. The physician will receive notification that these orders have been entered and are ready to review. A letter to the patient will be generated describing the physician's review of their information, prescription of a statin, and the risks and benefits of taking a statin medication.

--Intervention 2: Active choice and social comparisons—

The procedure listed above in intervention 1 will be used. In addition, physicians in this arm will receive social comparisons feedback on their statin prescribing behavior as follows: Those below the median will be told the statin prescribing rate for the average (50th percentile). Those above the median but below the top performers will only be told the prescribing rate of the top performers. Those above the 90th percentile will be told they are a top performer.

5.2 Study duration

The study is expected to begin in February 2017 and take one year to complete.

5.3 Target population

Patients followed by primary care physicians at the University of Pennsylvania Health System who using evidence-based guidelines are eligible to be prescribed a statin.

5.4 Accrual

Primary care physicians at the University of Pennsylvania Health System will be randomly assigned to one of the three arms. Based on an initial data review, we have made the following assumptions: baseline statin initiation rate is about 65%, median number of patients eligible but not on a statin per primary care physician is 38, intracluster correlation for statin prescribing is 0.026. Given these baseline, we estimate that a sample size of 84 primary care physicians (28 per arm) will provide at least 90% power to detect a 10% difference between each intervention arm and the control arm, using a Bonferroni correction to define an alpha of .017 (three comparisons) as our threshold for statistical significance.

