8.2 Procedures

Data on primary care physicians and their patients at the University of Pennsylvania Health System will be obtained from Penn Data Store and Clarity (Epic's data reporting database). Physician data includes demographic information (age, race, gender, type of medical degree, etc.) and may be also obtained from publicly available databases or websites online. Patient information includes demographic information, information about comorbid conditions (including diabetes, hypertension, and chronic kidney disease, and comorbid conditions needed to calculate the Charlson Comorbidity Index, laboratory test results (total cholesterol, triglycerides, LDL-C, HDL-C, liver function tests, creatinine, and glomerular filtration rate), and any contraindications to statin prescription (allergies or history of adverse reactions).

After identifying eligible physicians and patients, block randomization will occur at the physician level using block sizes of three and stratifying by quartile of baseline statin prescribing rate.

9. Analysis plan

In the main analysis, we will perform unadjusted comparisons of the change in the percent of eligible patients that are prescribed a statin before and after the intervention by study group using chi-square tests. To evaluate the robustness of the findings, a multivariate logistic regression

model will be fit adjusting for baseline statin prescription status as well as patient and physician factors. Binary variables will be created for time (pre- and post-intervention), study arm (control or intervention), and statin prescription (no or yes). The outcome of interest will be the interaction between the binary variables time, study arm, and statin prescription. All hypothesis tests will be two-sided using an alpha of 0.017 as our threshold for statistical significance. Clustering will be conducted at the level of the physician.

10. Investigators

[name], MBA, MS is the Principal Investigator (PI) and is an Assistant Professor of Medicine and Health Care Management at the Perelman School of Medicine and The Wharton School at the University of Pennsylvania. He has past experience leading clinical trials to deploy interventions impacting patient care and outcomes. He currently spends 80% of his effort on research and 20% on clinical and teaching activities.

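### Optional, low-cost improvement (not an error): Holm's procedure in place of a flat 0.017 for the three comparisons would add some power at the same sample size, by an amount that depends on the pattern of effects

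*Combined protocol and SAP*

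**What the plan says.** Section 5.4 (Accrual) sets the threshold by "using a Bonferroni correction to define an alpha of .017 (three comparisons) as our threshold for statistical significance". The power claim there is at least 90% for a "10% difference between each intervention arm and the control arm". This names the two control contrasts. The third comparison is not listed.

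Section 9 (Analysis plan) applies the same rule: "All hypothesis tests will be two-sided using an alpha of 0.017 as our threshold for statistical significance". The main analysis compares the change "before and after the intervention by study group using chi-square tests". The section closes with "Clustering will be conducted at the level of the physician", without saying whether that covers the chi-square tests or only the regression. No stepwise procedure appears in either section, and the two sections agree with each other.

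**The concern.** A flat Bonferroni threshold holds every comparison to the strictest level, even after another comparison has succeeded. Holm's procedure orders the three p-values. It tests the smallest against 0.05/3, the next against 0.025 and the last against 0.05, and stops at the first failure. It rejects everything that Bonferroni at 0.05/3 rejects, and sometimes more. Its 5% bound needs no assumption about how the tests are correlated, so the shared control arm is no obstacle, and the rule works whichever three comparisons are meant.

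What is at stake is modest. The trial asks whether active choice works both with and without social comparison feedback, so showing that both arms beat control is a natural goal. The flat rule gives up some power for that second finding and gets simpler interval estimates in return.

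**Working it through.** **Inputs, all from section 5.4.** 28 physicians per arm; 38 patients per physician; intracluster correlation 0.026; baseline rate 65%; difference 10 points, taken here as 65% vs 75%; two-sided alpha 0.017. The third comparison is assumed to be intervention 1 vs intervention 2.

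**Step 1: the plan's own power figure.**
- Design effect = 1 + (38 − 1) × 0.026 = 1.962.
- Effective patients per arm = 28 × 38 / 1.962 = 1064 / 1.962 = 542.3.
- Standard error of a difference = √[(0.65 × 0.35 + 0.75 × 0.25) / 542.3] = √(0.415 / 542.3) = 0.02766.
- Standardised effect = 0.10 / 0.02766 = 3.615; critical value for two-sided 0.017 = 2.387.
- Power = Φ(3.615 − 2.387) = Φ(1.228) = 89.0% (88.8% with a pooled null variance).

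This is close enough to the stated 90% to treat the inputs as the ones the plan used.

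**Step 2: flat 0.017 against Holm on the same simulated trials.** Two million draws of three arm proportions with effective n 542.3 and all three pairwise z-tests. Rates are control / intervention 1 / intervention 2, here 65/75/75:

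| Quantity | Flat 0.017 | Holm |
|---|---|---|
| Each control comparison | 89.0% | 90.9% |
| Both control comparisons | 82.1% | 86.0% |
| At least one rejection | 96.0% | 95.9% |
| False rejection of the remaining true null (1 vs 2) | 1.7% | 4.2% |

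The tiny fall in the third row arises because 0.05/3 = 0.01667 is just below 0.017. By the formula in step 1, the flat rule would reach 90.9% with 29.7 physicians per arm, so Holm is worth nearly two physicians per arm in this scenario.

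A physician-level check (200,000 beta-binomial trials, t-tests on physician proportions with 54 degrees of freedom) gives the same picture: each 87.0 to 89.3%, both 78.6 to 83.3%, at least one 95.5 to 95.4%, remaining true null 1.7 to 4.1%.

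**Step 3: other effect patterns.** Gain on the 10-point contrast with control, where flat power is 89% throughout:

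| Assumed rates | Gain under Holm |
|---|---|
| 65/70/75 | about 0.3 points |
| 65/72/75 | about 0.5 |
| 65/67/75 | about 1 |
| 65/65/75 | about 2 |
| 65/75/80 | about 5 |

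The 10-point contrast gains only when another comparison has already been rejected. At 65/75/80 the 15-point contrast is nearly always rejected first, which relaxes the threshold for the 10-point one. At 65/70/75 the 10-point contrast is itself usually the first tested, so it gains little. The 5-point control contrast in that scenario gains more, from about 27% to 34%.

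**Step 4: where flat power is already near its ceiling.** At assumed rates 10/20/20, each control comparison goes from 98.8% to about 99.2–99.3% (+0.4), and both gain about 0.9 points. The remaining true null is rejected in 4.8% of trials.

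**Step 5: gain by flat-rule power.** This depends less on the outcome scale. It assumes equal effects in the two interventions and equal variances:

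| Flat power | Each under Holm | Both, flat to Holm |
|---|---|---|
| 60% | 62.9% | 43.9 to 50.0% |
| 80% | 82.7% | 68.7 to 74.2% |
| 90% | 91.9% | 83.3 to 87.1% |
| 95% | 96.2% | 91.2 to 93.6% |

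**Step 6: family-wise error with no true effects (65/65/65).** 4.5% under the flat rule and 4.4% under Holm.

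**The case against.** The strongest reply is that this is a preference. The flat rule is valid, stated alike in both sections, and comes with intervals that agree with the tests. All of that stands, and it is why the point is optional.

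A second reply is that a quoted gain of 2 and 4 points belongs to one scenario. That also stands: step 3 shows a range of about 0.3 to 5 points for the same contrast, and step 4 shows less than 1 point at high power. The scenario itself is uncertain. Section 5.4 pairs a "baseline statin initiation rate is about 65" per cent with a cluster size described as "median number of patients eligible but not on a statin per primary care physician is 38", so the rate in the analysed patients may not be 65%. The outcome in section 3.1 is "the change in percentage of eligible patients prescribed a statin medication within 2 months of intervention completion", which the proportions above do not model.

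Third, Holm relaxes protection for whichever null remains true. If both interventions work equally well, that null is the question of whether social comparison adds anything. The rise from 1.7% to 4–5% is a real cost, though it stays within 5%.

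Fourth, the guarantee needs p-values that allow for clustering, and section 9 leaves this unclear for the chi-square tests. So the wording change is the whole cost only if that is settled. The same condition applies to the flat rule.

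A reader might infer that the flat 0.017 is a mistake, or that it inflates error because 3 × 0.017 = 0.051. The documents do not support this. The excess over 0.05 is rounding in an upper bound, and the simulated error is 4.5%.

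**Conclusion.** The point holds as a cheap improvement. At the planned sample size Holm is more powerful than the flat 0.017 while keeping family-wise error at or below 5%. On the plan's inputs and assumed rates of 65/75/75, the gain is about 2 points per control comparison and 4 points for both. Elsewhere it ranges from under half a point to about 5 points per 10-point contrast.

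Holm does not raise the chance of finding at least one effect, so it should not be presented as rescuing an underpowered trial. Nor is there a fixed gain to promise, since the size depends on the true effects and on the power of the before-after test finally used. The conclusion that Holm is valid rests only on valid, cluster-adjusted p-values. The sizes rest on the assumed rates, on the third comparison being intervention 1 vs 2, and on post-period proportions standing in for the change outcome.

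**What to change.** In sections 5.4 and 9, replace the fixed 0.017 with a sentence such as: *The three p-values are ordered and tested by Holm's procedure against 0.05/3, 0.025 and 0.05 (unrounded).* State that the p-values account for clustering by physician, including those from the main analysis. Naming the third comparison would help the reader, but Holm's validity does not depend on it.

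Report 98.3% confidence intervals (100 − 5/3) beside the Holm-adjusted p-values, and note that an interval may include zero for a comparison that Holm rejects.

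The cost is one sentence in each section, with no change to sample size, data collection or procedures. What is lost is the exact match between intervals and decisions, and some protection for a remaining true null. If the sponsor values those more, keeping the flat rule is a sound choice.
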